HIPAA	Health Insurance Portability and Accountability Act
IB	Investigator's Brochure
IRB	Institutional Review Board
PHI	Protected Health Information
PI	Principal Investigator
RAS	Recurrent Aphthous Stomatitis
SAE	Serious Adverse Event/Serious Adverse Experience
SOP	Standard Operating Procedure

Study Summary

Title	A Pilot Study Evaluating the Efficacy of Apremilast in the Treatment of Subjects with Severe Recurrent Aphthous Stomatitis (RAS)
Running Title	A Pilot Study on the use of apremilast for Recurrent Aphthous Stomatitis (RAS)
Protocol Number	N/A
Phase	Pilot
Methodology	
Overall Study Duration	24 weeks
Subject Participation Duration	24 weeks
Single or Multi-Site	Single Site
Objectives	Determination of treatment efficacy and safety of Apremilast in patients with RAS
Number of Subjects	15
Diagnosis and Main Inclusion Criteria	Males and females, between 18 and 70 years old, with Recurrent Aphthous Stomatitis (RAS)
Study Product, Dose, Route, Regimen	Apremilast 30mg orally twice daily for 16 weeks
Treatment duration	Sixteen weeks on active study. Posttreatment follow-up period of 8 weeks.
Statistical Methodology	Wilcoxon signed rank test for comparison of outcomes between treatments and McNemar's exact test for categorical outcome variables

1 Introduction

This document is a protocol for a human research study. This study will be carried out in accordance with the applicable federal regulations and Mayo Clinic research policies and procedures.

1.1 Background

Recurrent aphthous stomatitis (RAS), or canker sores, represents a very common mucosal disorder, occurring in men and women of all ages, races and geographic regions and affecting up to 60% of North Americans.¹ The word 'aphthous' originates from the Greek word aphtha referring to an ulcer of the mucosal surface and 'stomatitis' refers to inflammation of the oral mucosa. Patients suffer from simple aphthosis, meaning they develop only occasional canker sores a few times per year which are a nuisance, but are not otherwise a difficult problem.

However, a subset of individuals with RAS suffer from a severe variant with persistent, refractory ulcers which may be present more often than not. This subset of canker sore sufferers tend to have more painful, persistent canker sores which may be larger, with multiple lesions occurring synchronously. These ulcers can take several weeks to heal, and as one episode resolves, another bout of ulcers develops. Patients often have ulcers present more than 50% of the time, and go from one episode of aphthosis into another so that they are seldom ulcer free.

Severe RAS (ulcers present more often than not/multiple, large ulcers/present synchronously/ slow to heal) – is sometimes referred to as "complex aphthosis" a term suggested by Jorizzo and Rogers², experts in the field of oral dermatology. Such patients are otherwise healthy, with no systemic disease and few to no comorbid conditions. It is thought that this phenomenon may represent an "up regulation" of the immune system.³ Attacks of RAS may be precipitated by local trauma, stress, food intake, drugs, hormonal changes and vitamin and trace element deficiencies.¹ Local and systemic conditions, and genetic, immunological and microbial factors all may play a role in the pathogenesis of RAS.¹

1.2 Investigational Agent

Otezla (apremilast) 30mg.

1.3 Clinical Data to Date

To date, no principal cause for RAS has been established. The lesions of RAS are painful and disabling to many patients and there are a large number of patients who seek treatment for this debilitating condition. Unfortunately, the disorder is not well understood and often managed by generalists or oral surgeons. Since the etiology is unknown and there are no specific diagnostic tests, the diagnosis is based on history and clinical criteria. The long-term prognosis for patients with severe RAS is excellent because with time and increasing age, the condition may remit. However, patients may face 10 to 15 years of recurrent aphthosis and hence, treatment during this phase is warranted, to improve the severity of oral ulcers.¹

By way of clarification, – severe RAS (or complex aphthosis) – is quite discrete from Behçet's disease, which also is characteristically associated with oral ulceration. In contradistinction, Behçet's disease is a rare, chronic, multisystemic disorder characterized by mucocutaneous, ocular, vascular and central nervous system

6/21/2017

manifestations, and is thought to be a systemic vasculitis.⁴ The clinical spectrum is wide and may include oral and genital ulcers among the many clinical features. The etiopathogenesis of Behçet's disease remains unknown, although genetic predisposition, environmental factors and immunological abnormalities have been implicated.⁵ The prognosis of Behçet's disease is very different and may be guarded depending on the extent of the systemic vasculitis and treatment may be lifelong. Despite the distinction between severe RAS and Behçet's disease, it is postulated that treatments that attenuate the mucosal manifestations of Behçet's may also be effective in management of severe RAS.

A phase 2, double-blind, placebo-controlled study was published in 2015 which demonstrated apremilast to be effective in treating the oral ulcers manifested in Behçet's disease.⁶ Given that oral ulcers are the cardinal manifestation of Behçet's disease, it has been suggested that apremilast may also be effective in patients with severe RAS.

1.4 Dose Rationale and Risk/Benefits

Based on the safety and efficacy of previous studies using apremilast for Behçet's disease and psoriasis, the dose of apremilast 30mg was chosen for the present study. Subjects will receive apremilast 30mg twice daily for 16 weeks. Since apremilast is known to be associated with gastrointestinal side effects and headaches, the dose will be increased gradually during the first week of treatment until the full 30mg dose is reached.

The expected benefits from apremilast use include reduction in the number and duration of oral ulcers, decreased oral ulcer pain, improved physical function and quality of life in patients with RAS. Risks associated with apremilast therapy include possible gastrointestinal side effects, headaches, upper respiratory tract infection, hypersensitivity reactions and depression.

2 Study Objectives

Primary Objective

- To evaluate the efficacy of apremilast for the treatment of RAS.

Secondary Objectives

- To evaluate the safety and tolerability of apremilast in subjects with RAS.

3 Study Design

3.1 General Design

The study will be a pilot study using apremilast 30mg orally twice daily, for treatment of RAS in males and females between 18 and 70 years old.

Subjects will be recruited from the clinical practice of the Department of Dermatology or Division of Rheumatology at Mayo Clinic Florida. Fifteen males and females with RAS will be enrolled.

The study will consist of 3 phases: a screening phase, a 16 week treatment phase and an 8 week posttreatment observational follow-up phase.

The screening phase will consist of: obtaining informed consent, demographic information, medical history, inclusion and exclusion criteria, prior and concomitant medication use, adverse events; collecting vital signs and weight; performing complete physical examination and limited physical examination; obtaining hematology, serum chemistry, urinalysis, pregnancy test and providing contraception education.

During the 16-week treatment phase, all subjects receive apremilast.

All subjects who complete the active treatment phase are to enter the 8-week posttreatment observational follow-up phase.

3.1.1 Contraception Education

The risks to a fetus or to a nursing child from apremilast are not known at this time. Results of the animal and in vitro studies can be found in the IB.

All females of childbearing potential (FCBP) must use one of the approved contraceptive options as described in section 4.1.1 while on investigational product (IP) and for at least 28 days after administration of the last dose of the IP.

When a female subject of childbearing potential's contraceptive measures or ability to become pregnant changes at the time of study entry or at any time during the study, the Investigator will educate the subject regarding options and correct and consistent use of effective contraceptive methods in order to successfully prevent pregnancy.

3.2 Study population

Male and female subjects between 18 and 70 years old at the time of consent, who have diagnosis of RAS and who have had at least 2 oral ulcers in the 4 weeks prior to enrollment at baseline.

3.3 Primary Study Endpoints

Improvement in the following parameters of the RAS lesions: %change in the number of ulcers at the end of treatment, duration of ulcers and duration of the remission period between ulcer episodes.

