4.1 Inclusion Criteria

1. Male and female subjects between 18 and 70 years of age
2. Oral ulcers that occurred at least monthly in the 6 month period prior to enrollment
3. Had at least 2 oral ulcers in the 4 weeks prior to enrollment at baseline
4. At least 3 oral ulcers during an ulcer flare
5. Patients must be candidates for systemic therapy for the treatment of oral ulcers, those that are considered unsuitable for topical therapy alone based on severity of disease, or whose oral ulcers cannot be adequately controlled with topical therapy.
6. Female premenopausal subjects must use one of the approved contraceptive options while taking apremilast and for at least 28 days after administration of the last dose of apremilast
7. Patients are able and willing to provide written informed consent after the nature of the study is fully explained.
8. No evidence of systemic disease

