6.2 Sample Size Determination

A total of 15 patients will be enrolled in this study. This sample size will be sufficient in order to gain valuable data that could be used in the design of a future, larger study. Given the pilot/feasibility nature of the study, no formal power calculations were performed.

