6.3 Statistical Methods

Data Analysis – Given the design, all statistical analysis will be descriptive. Continuous outcome measures will be summarized using the sample mean, standard deviation, median, minimum, 25th and 75th percentiles, and maximum. Categorical variables will be summarized with number and percentage. 95% confidence intervals (CIs) will be estimated where appropriate.

Descriptive Statistics

We will summarize continuous variables using the sample mean, standard deviation, median, minimum, 25th and 75th percentiles, and maximum. We will summarize categorical variables with number and percentages. Ordinal variables will be summarized using the sample median, minimum, 25th and 75th percentiles, and maximum, as well as with number and percentage.

Handling of Missing Data

Given the prospective nature of the study, we expect to encounter little if any missing data. However in the event of missing data, no attempt to impute this missing data will be made in this pilot study; missing data will be treated as missing.

Multiplicity

No adjustment for multiple testing will be made owing to the exploratory, pilot nature of the study.

Primary Hypothesis:

We hypothesize that apremilast administration for RAS will decrease the number of ulcers at the end of treatment compared to baseline.

The primary endpoints of the study is the change in number of ulcers at the end of treatment compared to baseline.

The secondary endpoints of the study, occurrence of adverse reactions and morbidity, are both dichotomous categorical variables. As such, the proportion for which these outcomes occur will be estimated along with 95% confidence interval.

Interim Analysis

No interim analysis will be performed in this pilot study.

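### Sections 3.3 and 6.3 name different primary measures of ulcer number, and a mean of individual percent changes on small counts sits above the percent change in total ulcers and is noisier

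*Combined protocol and SAP*

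**What the plan says.** Section 3.3 opens its list of primary parameters with percent change in ulcer number; the percent sign stands directly before "change in the number of ulcers at the end of treatment". Section 6.3 drops the percent: "The primary endpoints of the study is the change in number of ulcers at the end of treatment compared to baseline".

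For summaries, section 6.3 states: "Continuous outcome measures will be summarized using the sample mean, standard deviation, median, minimum, 25th and 75th percentiles, and maximum". It adds 95% CIs where suitable and says that "all statistical analysis will be descriptive". The Study Summary names a "Wilcoxon signed rank test for comparison of outcomes between treatments", which section 6.3 does not repeat. Neither section says how percent change is calculated or pooled, or which summary leads.

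Two entry criteria in section 4.1 concern ulcer counts: "Had at least 2 oral ulcers in the 4 weeks prior to enrollment at baseline" and "At least 3 oral ulcers during an ulcer flare". The first covers a four-week window and the second a flare. Neither sets a minimum for the count at the week 0 visit.

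On size, section 6.2 says "A total of 15 patients will be enrolled in this study". It gives no power calculation and says the data are meant to help design a larger study. Section 3.1 has every subject on apremilast, so the only contrast is within patient.

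**The concern.** An individual percent change cannot fall below -100% but has no upper limit. A patient going from 3 ulcers to 1 scores -67%; one going from 1 to 3 scores +200%. In ulcers these two cancel; as percentages they average +67%. Patients with the fewest baseline ulcers therefore dominate the mean and its SD.

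A statistician following sections 3.3 and 6.3 as written would report that mean, its SD and possibly a CI for a measure the protocol calls primary. The result can point the opposite way from the change in ulcer number that section 6.3 calls primary. The effect size and SD could also pass into the design of the later study.

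**Working it through.** The plan gives no effect size, SD or power, so there is no figure of its own to reproduce.

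**Inputs from the documents:** n = 15, one arm, mean and SD listed, no minimum visit count. **Assumptions, because the documents give no count distribution:** Poisson visit counts with mean λ; baseline X and week 16 count Y independent given the patient's rate; baseline at least 1 (percent change is undefined at 0); true reduction e; optionally gamma variation between patients (shape 4, CV 0.5).

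**1. Arithmetic that needs no distribution.** Twelve patients go from 4 to 2 ulcers and three go from 1 to 4.
- Mean of individual percent changes: (12 × (-50) + 3 × 300)/15 = +20%.
- Totals: baseline 12 × 4 + 3 × 1 = 51; end 12 × 2 + 3 × 4 = 36; 36/51 - 1 = -29%.
- Median individual percent change: -50%.

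**2. Expected values.**
- Mean of individual percent changes: 100 × (λ(1-e) E[1/X | X≥1] - 1).
- Percent change of group means: 100 × (λ(1-e)/E[X | X≥1] - 1).

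For λ = 3, E[1/X | X≥1] = 0.4327 and E[X | X≥1] = 3/(1 - exp(-3)) = 3.157. With e = 25%, the first is 100 × (3 × 0.75 × 0.4327 - 1) = -2.6% and the second is 100 × (2.25/3.157 - 1) = -28.7%. Each cell below gives mean of individual changes / group figure, in percent:

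| λ | no effect | 25% reduction | 50% reduction |
|---|---|---|---|
| 2 | +15.3 / -13.5 | -13.5 / -35.2 | -42.3 / -56.8 |
| 3 | +29.8 / -5.0 | -2.6 / -28.7 | -35.1 / -52.5 |
| 4 | +31.9 / -1.8 | -1.1 / -26.4 | -34.1 / -50.9 |
| 6 | +24.7 / -0.2 | -6.5 / -25.2 | -37.7 / -50.1 |

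Because E[1/X] exceeds 1/E[X], the first figure is always the higher in expectation here. It was also higher in every gamma scenario run. With gamma variation at λ = 2 the 25% case averages about -18%, the lower end of the range.

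**3. Simulated 15-patient trials, true 25% reduction.** With gamma variation and mean 3, the mean of individual changes averages about -10%, with a standard error of about 24 points against about 15.5 for the ratio of totals. It is zero or positive in 31% of trials, against 5%. In 26% of trials it is zero or positive although the mean number of ulcers fell. Over means 2 to 6, with and without between-patient variation, the two probabilities run about 21-44% and 3-6%.

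**4. Sensitivity to the baseline floor, no true effect** (same formulas, conditioning on the floor; λ = 2, 3, 4):
- Baseline at least 2: mean of individual changes -23, -2, +10%; group figure -31, -16, -7.5%.
- Baseline at least 3: -43, -22, -7%; group figure -46, -28, -16%.
- Baseline at least 1 but λ = 1: -23%; group figure -37%.

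Selecting on a high baseline count pulls both measures down, and the ratio of totals is pulled further.

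**The case against.** Several points on the other side stand.

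- **Direction.** A reader might infer that the mean of percent changes is biased upward against the true effect in general. The documents do not support that. They give no count distribution, and the two entry criteria are minimums over a window and a flare, not typical visit counts. If every baseline were at least 2 with λ = 3, the mean would be -2, -26.5 and -51% for true reductions of 0, 25 and 50%, which is nearly unbiased, and the chance of a non-negative mean at a 25% reduction would be about 5%.
- **The replacement is not unbiased.** In that same case the ratio of totals gives -16, -37 and -58%. A bootstrap interval at n = 15 (λ = 3, reductions of 25% and 50%) covered about 92% and 90%, not 95%.
- **Partly handled already.** Section 6.3 lists the median and quartiles beside the mean and names absolute change as primary. The Study Summary names a rank test. Nothing makes the mean of percent changes the headline.
- **Limited consequence.** The analysis is descriptive, with no decision rule.

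These points narrow the claim but do not remove it. Section 3.3 still calls percent change primary, section 6.3 still attaches a mean, SD and possibly a CI to it, and a visit count of 1 is not excluded. A rank test supplies no effect size to replace them.

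**Conclusion.** The two sections disagree on the primary measure of ulcer number. If percent change is averaged over patients, the result is on average higher than the percent change in totals and less precise. With Poisson means of 2 to 6 and baselines of at least 1, a true 25% reduction averages about -1% to -18% and often shows no fall at n = 15.

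A reader might go further and infer that an effective drug would look inactive. That holds only for modest effects, of roughly 20-30%: at a 50% reduction the mean still falls by about 34% or more, and for means of 2 to 4 it is non-negative in at most about 5% of trials. Even so, a 50% effect reported as -34% is understated by about a third, (50 - 34)/50 = 32%, which matters for a pilot meant to inform a larger study.

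All sizes rest on assumed counts. If visit counts are all at least 2 or 3, or the mean count is near 1, regression to the mean can put both measures below the truth, and no summary of a single arm removes that. The change is worth making because it is cheap; it is not a fatal flaw.

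**What to change.** In sections 3.3 and 6.3:

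1. State the absolute change in number of ulcers from baseline to end of treatment as the one primary summary of ulcer number, in the same words in both places.
2. Define the percent figure as 100 × (sum of end-of-treatment counts / sum of baseline counts - 1) over the same patients, with a 95% CI from a bootstrap that resamples patients, described as approximate at n = 15.
3. Show individual percent changes only by median, quartiles and a listing, without mean, SD or t-interval.
4. State that regression to the mean remains in a single-arm comparison and is not removed by this choice.

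The cost is a few sentences of wording and a line or two of code; no new data or visits are needed. The downside is that patients with more baseline ulcers get more weight in the group percent figure.

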5.4 Prior and Concomitant Therapy

Subjects will be allowed the following concomitant therapies to control flares: Tylenol, lidocaine 2% topical mouth wash and lidocaine 2% plus diphenhydramine plus Maalox topical mouth wash.

No topical and systemic therapies for RAS may be used 3 months prior to study enrollment.

6 Study Procedures

- a. The screening phase will consist of: obtaining informed consent, demographic information, medical history, inclusion and exclusion criteria, prior and concomitant medication use, adverse events; collecting vital signs and weight; performing complete physical examination, hematology, serum chemistry (vitamins B1, B6, B12, C, iron, folate, zinc, TTG, ANA), urinalysis, pregnancy testing, contraception education. Patients will also be assessed in regards to number of oral ulcers and pain visual analog scale for oral ulcers. A diary will be provided to the patient for keeping record of number and pain intensity of oral ulcers throughout the study.
- b. At baseline (week 0) all patients will undergo a complete medical history and limited physical examination, suitability assessment (inclusion and exclusion criteria), and safety assessments (adverse events, vital signs, weight, contraception education). Patients will also be assessed in relation to number of oral ulcers, pain visual analog scale for oral ulcers, physician's global assessment of oral lesions and Chronic Oral Mucosal Disease Questionnaire – COMDQ) and the investigational product will be dispensed.
- c. At week 2 all patients will undergo safety assessments (adverse events, vital signs, weight, and contraception education), efficacy assessments (number of oral ulcers, pain visual analog scale for oral ulcers, physician's global assessment of oral lesions) and investigational product accountability.
- d. At week 4 all patients will undergo safety assessments (adverse events, vital signs, weight, and contraception education), efficacy assessments (number of oral ulcers, pain visual analog scale for oral ulcers, physician's global assessment of oral lesions) and investigational product accountability. The investigational product will be dispensed.

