- e. At week 8 all patients will undergo safety assessments (adverse events, vital signs, limited physical examination, weight, contraception education, and optional lab work per Investigator's discretion, including hematology and serum chemistry), efficacy assessments (number of oral ulcers, pain visual analog scale for oral ulcers, physician's global assessment of oral lesions and Chronic Oral Mucosal Disease Questionnaire – COMDQ) and investigational product accountability. The investigational product will be dispensed.
- f. At week 12 all patients will undergo safety assessments (adverse events, vital signs, weight, and contraception education) and efficacy assessments (number of oral ulcers, pain visual analog scale for oral ulcers and physician's global assessment of oral lesions) and investigational product accountability. The investigational product will be dispensed.
- g. At week 16 all patients will undergo safety assessments (adverse events, vital signs, weight, complete physical examination, contraception education and optional lab work per Investigator's discretion, including pregnancy testing, hematology and serum chemistry), efficacy assessments (number of oral ulcers, pain visual analog scale for oral ulcers, physician's global assessment of oral lesions and Chronic Oral Mucosal Disease Questionnaire – COMDQ) and investigational product accountability.
- h. At week 24 patients will undergo safety assessments (vital signs, weight, and complete physical examination) and efficacy assessments (number of oral ulcers, pain visual analog scale for oral ulcers, physician's global assessment for oral lesions and Chronic Oral Mucosal Disease Questionnaire - COMDK).

6/21/2017

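### Ulcer duration and remission duration are listed as primary in 3.3, but 6.3 omits them and the specified records carry no ulcer dates or diary frequency, so individual ulcer durations cannot be derived

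*Combined protocol and SAP*

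**What the plan says.** **Endpoints.** Section 3.3 seeks improvement in three primary parameters: percentage change in ulcer number at the end of treatment, and "duration of ulcers and duration of the remission period between ulcer episodes". Section 6.3 states: "The primary endpoints of the study is the change in number of ulcers at the end of treatment compared to baseline". Its hypothesis also concerns ulcer number only; neither duration appears in 6.3.

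**Data capture.** Section 6, item a: "A diary will be provided to the patient for keeping record of number and pain intensity of oral ulcers throughout the study". No entry frequency is given. Section 6 and the schedule in 6.1 list ulcer number, pain VAS, physician's global assessment and, at some visits, COMDQ. There is no item for onset, healing or individual ulcers. Section 8.1 should list the variables but holds only a template prompt.

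**Follow-up.** Section 3.1: "All subjects who complete the active treatment phase are to enter the 8-week posttreatment observational follow-up phase". Ulcers are counted again at week 24.

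**Analysis.** Section 6.3 is generic: "Continuous outcome measures will be summarized using the sample mean, standard deviation, median, minimum, 25th and 75th percentiles, and maximum". The Study Summary adds a "Wilcoxon signed rank test for comparison of outcomes between treatments", without naming an endpoint or time points. For missing values, 6.3 says that "missing data will be treated as missing". Nothing addresses intervals still open at the end of observation.

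**The concern.** Two of the three parameters that 3.3 calls primary depend on dates that the plan does not ask anyone to record, and the statistical section does not take them up. Overlap and succession of ulcers are expected in this population: 4.1 requires at least 3 ulcers during a flare, and 1.1 describes one bout giving way to another. Those are the conditions in which counts do not determine durations.

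At stake is whether the durations can be reported at all in a reproducible way. Section 6.2 justifies the 15 patients by the data they will supply for designing a larger study, and dates not recorded at the time cannot be reliably recovered later.

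**Working it through.** The plan states no figure for these endpoints, so there is none to reproduce. The check asks what the specified records can identify.

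**1. Ulcer duration from daily counts (the most generous reading of the diary).** Summed daily counts give total ulcer-days, and mean duration = ulcer-days / number of distinct ulcers. Counts do not give that denominator when one ulcer heals as another starts.

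- Ten days at count 3 is 30 ulcer-days. Three ulcers: 30/3 = 10 days. Six ulcers (all three replaced after day 5): 30/6 = 5 days. A single replacement already gives 30/4 = 7.5 days.
- Counts 1,2,3,3,2,1 fit ulcers on days 1–6, 2–5 and 3–4 (durations 6, 4, 2) or on days 1–4, 2–5 and 3–6 (4, 4, 4). The mean is 4 both times; the SD is 2 or 0 and the maximum 6 or 4.
- Counts 1,1,2,2,1,1,1,1,1,1 fit ulcers on days 1–4 and 3–10 (durations 4, 8) or on days 1–10 and 3–4 (10, 2). The mean is 6 both times; the SD is 2.83 or 5.66.

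So replacement changes the mean, while overlap without replacement changes only the spread.

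**2. Remission length.** A daily count identifies ulcer-free days, so a daily diary would give remission length once remission is defined. Without one, the visits are what remains. Visit days are 0, 14, 28, 56, 84, 112 and 168, with gaps of 14, 14, 28, 28, 28 and 56 days.

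- Ulcers at week 4, none at week 8, ulcers at week 12: a single remission of anywhere from 1 to 84 − 28 − 1 = 55 days.
- Ulcers at week 12, none at week 16, ulcers at week 24: 1 to 168 − 84 − 1 = 83 days.

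These ranges apply only if diary entries do not fill the gaps.

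**3. Open intervals.** The case report in 1.3 describes clearance within 6 weeks (day 42) and no recurrence over 12 months. Such a patient has a remission still open after at least 112 − 42 = 70 days at week 16 and at least 168 − 42 = 126 days at week 24. An ulcer still present at the last observation is censored in the same way.

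**4. Direction of bias if only completed remissions were averaged.** The documents give no remission or episode lengths, so the following are assumptions: exponential remissions, 10-day ulcer episodes, no drug effect, and observation starting at an arbitrary point in the cycle. Simulated mean completed remission:

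| True mean | 28-day window | 112-day window |
|---|---|---|
| 14 days | about 7 | about 12 |
| 28 days | about 8 | about 20 |

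Both windows understate the true mean, the shorter one more. Comparing a 28-day pre-dose window with 112 days of treatment would show a gain of about 5 or 12 days with no effect at all. Windows of equal length would not create this artefact. The plan defines neither window, so the sign for the change from baseline is undetermined.

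**The case against.** The strongest defence is that this is a 15-patient descriptive pilot with no power calculation, whose hypothesis concerns ulcer count only. The diary runs throughout the study and is handed out at screening, so a site that asked for daily entries would obtain remission lengths and probably some pre-dose data. The summaries in 6.3 cover all continuous outcomes, and the ulcer count receives no endpoint-specific method there either. Most of this stands, and it rules out several stronger conclusions that a reader might draw:

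- *Neither duration can be measured.* Too strong for remission, where the defect is the unstated entry frequency and the missing definition.
- *There is no baseline and no analysis.* Pre-dose entries may exist, and the generic summaries or the Wilcoxon test could be applied. What is missing is a named comparator period and a defined variable.
- *Open remissions will be dropped and benefit understated.* The plan does not say that an open remission counts as missing. If it did, the on-treatment mean would be shortened, but 3.3 asks for improvement, and step 4 shows that the change can be biased the other way.
- *The trial's main result is compromised.* The ulcer count is collected at every visit and does not depend on any of this.

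The defence does not rescue individual ulcer durations. Daily entries alone do not identify them, and a generic summary cannot be applied to a variable that is not captured. Nor does it remove the disagreement between 3.3 and 6.3.

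**Conclusion.** The point holds as a gap in specification and a contradiction between 3.3 and 6.3. Followed as written, the plan does not yield individual ulcer durations; identical daily counts can correspond to a two-fold difference in mean duration (10 versus 5 days). It yields remission length only if the diary is kept daily or bouts are dated. Comparator and censoring rules are absent for both.

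The count examples are constructed patterns showing what counts cannot distinguish, not estimates of typical error. The simulation rests on assumed remission and episode lengths and shows only that the bias in a change score has no fixed direction. The effect on this trial's group summaries cannot be quantified from the documents. The change is worth making but does not threaten the ulcer-count endpoint.

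**What to change.** 1. Reconcile 3.3 with 6.3, for example with ulcer count primary and the two durations secondary.
2. Require daily diary entries from screening, with an onset and a healing date for each ulcer, and list these variables in 8.1.
3. Define episode and remission.
4. State how ulcers and remissions still open at the end of observation are censored, and whether weeks 16–24 count.
5. Report the durations descriptively. If a pre-dose diary period serves as comparator, name it and compare windows of equal length. State that regression to the mean is to be expected in a single-arm study that selects on recent ulcers (4.1 requires at least 2 in the 4 weeks before enrolment).
6. Optionally, add the percentage of ulcer-free days as a descriptive supplement for patients with diary data in the window. It remains defined when a patient clears, but it measures neither duration and should not replace them.

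The cost is protocol wording, a small change to the diary and slightly more recording by patients. Screening, whose length is not stated, may need to be longer if a pre-dose diary period is wanted.
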